#### **E. Database Protection**

The database will be secured with password protection. The manager will receive only coded information that is entered into the database under those identification numbers. Electronic communication with outside collaborators will involve only unidentifiable information.

#### **F. Management of Risks to Participants**

##### **Confidentiality**

Confidentiality of participant records will be secured by the use of study codes for identifying participants on CRFs, and secure storage of any documents that have participant identifiers on site, as well as secure computing procedures for entering and transferring electronic data. The documents or logs linking the study codes with the study participant on site will be kept locked separately from the study files and the medical records. No identifying information will be disclosed in reports, publications or presentations.

##### **Information That Meets Reporting Requirements**

The consent form will specifically state the types of information that are required for reporting and that the information will be reported as required. These include suspected or known sexual or physical abuse of a child or elders, or threatened violence to self and/or others.

## **Participant Protection**

AEs and concomitant medications will be assessed and documented at clinic visits. Individuals who experience an AE that compromises safe participation in the study will be discontinued from further intervention and provided referrals for other treatment or to specialized care. Study personnel will request that the participant complete an end visit to assure safety and to document outcomes.

## **Longterm Data Storage and Sharing**

Data for this project will be stored on University of Utah cloud computing servers and/or archives for long term-storage. Electronic access to these data are password protected, encrypted, and HIPAA compliant. Physical access will be protected by storage in locked cabinets inside locked facilities. Data will be de-identified before sharing with other investigators on a need to know basis, and on the agreement that once the data analysis is complete, the data will be returned or destroyed. Data will only be shared with investigators with appropriate data sharing agreements and/or Institutional Review Board for Human subjects approvals, as required.

## **13.0 DATA MANAGEMENT**

### **13.1 Design and Development**

The University of Utah site will be responsible for development of electronic case report forms (eCRFs), development and validation of the clinical study database, ensuring data integrity, and training site and participating staff at both sites on applicable data management procedures. This will also include the University of Utah site working to: 1) develop a data management plan and will conduct data management activities in accordance with that plan, 2) provide final guided source documents and eCRFs for the collection of all data required by the study, 3) develop data dictionaries for each eCRF that will comprehensively define each data element, 4) conduct ongoing data monitoring activities on study data from all participating sites, 5) monitor any preliminary analysis data cleaning activities as needed, and 6) rigorously monitor final study data cleaning. The remainder of this section provides an overview of the data management plan associated with this protocol.

### **13.2 Site Responsibilities**

The University of Utah will provide study leadership for data management, analysis, and reporting. The University of Utah will train staff at the University of Pittsburgh in data collection requirements, procedures, and security. Both sites will ensure before participant and other study data is uploaded to the data capture program, patient reported responses to interview questions are complete and accurate. Site audits will involve the University of Utah project coordinator reviewing uploaded study data to ensure completeness and accuracy of data. A trained University of Utah research staff member in day to day study operations will perform data reviews to ensure uploaded data from sites are complete and accurate.

### **13.3 Data Collection**

The data collection process consists of direct data entry at the study sites into the data capture program. In the event that the data capture program is not available, the University of Utah site will make available a final set of guided source documents and completion instructions. Data entry into the data capture program should be completed according to the instructions provided and project specific training. The investigator is responsible for maintaining accurate, complete and up-to-date records, and for ensuring the completion of the eCRFs for each research participant.

### **13.4 Data Editing**

Completed data will be entered into the data capture program. If incomplete or inaccurate data are found, a query will be generated to the sites for a response. Sites will resolve data inconsistencies and errors and enter all corrections and changes into the data capture program.

### **13.5 Data Transfer/Lock**

The University of Utah study statistician and statistical program will conduct final data quality assurance checks and “lock” the study database from further modification.

### **13.6 Data Quality Assurance**

To address the issue of data entry quality, the University of Utah will follow a standard data monitoring plan. An acceptable quality level prior to study lock or closeout will be established as a part of the data management plan. The management plan will entail the project coordinator generating regular data quality summaries during the course of the protocol. This will specifically involve building composite indicators and running descriptive statistics each month during participant recruitment and follow up.

## 14.0 APPENDIX A: ADVERSE EVENT REPORTING AND PROCEDURES

Each participating site's Principal Investigator is responsible for study oversight, including ensuring human research subject protection by designating appropriately qualified and trained study personnel to assess, report, and monitor adverse events. See AE form in the electronic data capture program.

### Definition of Adverse Events and Serious Adverse Events

An **adverse event** (AE) is any unexpected medical occurrence in humans, whether or not considered study intervention related which occurs during the conduct of a clinical trial. Changes from baseline in clinical status; i.e., death, miscarriage, pre-term birth, overdose, relapse, child protective services involvement including child removal; that are considered clinically significant by the study medical clinician are considered AEs.

**Suspected adverse reaction** is any adverse event for which there is a reasonable possibility that the study intervention caused the adverse event. A reasonable possibility implies that there is evidence that the study intervention caused the event.

**Adverse reaction** is any adverse event caused by the study intervention.

An **adverse event, suspected adverse reaction, or adverse reaction** is considered "**serious**" (i.e., a serious adverse event, serious suspected adverse reaction or serious adverse reaction) if, in the view of either the study medical clinician or sponsor, it:

- 1) Results in death: A death occurring during the study or which comes to the attention of the study staff during the protocol-defined follow-up period, whether or not considered caused by the study intervention, must be reported.
- 2) Is life-threatening: Life-threatening means that the study participant was, in the opinion of the medical clinician or sponsor, at immediate risk of death from the reaction as it occurred and required immediate intervention.
- 3) Requires inpatient hospitalization or prolongation of existing hospitalization.
- 4) Results in persistent or significant incapacity or substantial disruption of the ability to conduct normal life functions.
- 5) Is a congenital abnormality or birth defect.
- 6) Is an important medical event that may not result in one of the above outcomes, but may jeopardize the health of the study participant or require medical or surgical intervention to prevent one of the outcomes listed in the above definition of serious event.

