### **7.9.3 Breaking the Blind**

As the research assistant is the only blinded party, there is no scenario in which the blind will need to be broken. Investigators providing clinical management and decision-making are informed of each participants randomization result.

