## **8.2 Clinical and Safety Assessments**

### **8.2.1 Adverse Events (AEs) and Serious Adverse Events (SAEs)**

At each visit the study navigator assesses for AEs and SAEs by asking the study participant, "How have you been feeling since your last visit?" AEs and SAEs may also be spontaneously reported to study staff at any visit following consent. AEs and SAEs suggesting medical or psychiatric deterioration will be brought to the attention of a study clinician for further evaluation and management. Visits will emphasize overdose risk and risk-management. Any reported overdose is recorded as an AE or SAE, or in a separate form. AE and SAE reporting is according to the reporting definitions and procedures outlined in the protocol and in accordance with applicable regulatory requirements.

For the purpose of this study, the following AEs do not require reporting in the data system but is captured in the source documentation as medically indicated:

Grade 1 (mild) unrelated adverse events. This would typically include mild physical events such as headache, cold, etc., that were considered not reasonably associated with the study intervention.

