#### **B. Medical Monitor**

The site study clinician is responsible for reviewing all adverse events and serious adverse events reported. All SAEs will be reviewed at the time they are reported data capture program. The site clinician will also indicate concurrence or not with the details of the report provided by the site PI. Where further information is needed, the study clinician will discuss the event with the site staff. All AEs are reviewed on a regular basis to observe trends or unusual events.

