### Definition of Expectedness

Any adverse event is considered "unexpected" if it is not listed in the protocol, consent, or is not listed at the specificity or severity that has been observed.

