## **Site's Role in Eliciting and Reporting Adverse Events**

Appropriately qualified and trained personnel will elicit participant reporting of AEs and SAEs at each study visit designated to collect AEs. Adverse events (medical and/or psychiatric) assessment will initiate with participant consent and follow-up will continue through the final assessment. Study personnel will obtain as much information as possible about the reported AE/SAE to complete the AE/SAE forms and will consult as warranted.

Standard reporting, within 7 days of the site becoming aware of the event, is required for reportable AEs. Expedited reporting (within 24 hours of their occurrence and/or site's knowledge of the event) is required for reportable SAEs (including death and life-threatening events). Local sites are responsible for reporting SAEs to the IRB of record, per the IRB or record's guidelines.

Sites are required to enter reportable AEs and SAEs in data capture program. The AE form is used to capture reportable AEs and SAEs (as defined in the protocol) and will be reviewed by the study PI upon submission. Additional information may need to be gathered to evaluate SAEs and to complete the appropriate CRFs and the summary. This process may include obtaining hospital discharge reports, medical records, autopsy records or any other type records or information necessary to provide a complete and clear picture of the serious event and events preceding and following the event. If the SAE is not resolved or stable at the time of the initial report or if new information becomes available after the initial report, follow-up information must be submitted as soon as possible.

Reportable adverse events will be followed until resolution, stabilization or study end. Any serious adverse reactions will be followed until resolution or stabilization even beyond the end of the study.

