## **Site's Role in Assessing Severity and Causality of Adverse Events**

Appropriately qualified and trained study personnel will conduct an initial assessment of seriousness, severity, and causality when eliciting participant reporting of adverse events. A study medical clinician will review reportable AEs for seriousness, severity, and causality on at least a weekly basis.

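### Whether miscarriage, pre-term birth, child removal and other named harms become adverse events rests on an undefined, unmasked clinical-significance judgement, with no stated route or deadline for reaching the person who makes it

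*Combined protocol and SAP*

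**What the plan says.** Appendix A (section 14.0) defines an AE in two sentences. The first is general: an AE "is any unexpected medical occurrence in humans, whether or not considered study intervention related". The second names changes from baseline (death, miscarriage, pre-term birth, overdose, relapse, and child protective services involvement with child removal included) and states that those "that are considered clinically significant by the study medical clinician are considered AEs". The Definition of Expectedness then calls an event unexpected "if it is not listed in the protocol, consent, or is not listed at the specificity or severity that has been observed".

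Other statements bear on how these events are handled:

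- Section 8.2.1, overdose: "Any reported overdose is recorded as an AE or SAE, or in a separate form".
- Appendix A, severity and causality: "A study medical clinician will review reportable AEs for seriousness, severity, and causality on at least a weekly basis".
- Data and Safety Monitoring Plan (section 12.0), part B: "The site study clinician is responsible for reviewing all adverse events and serious adverse events reported". SAEs are reviewed when they are reported.
- Appendix A, eliciting and reporting: expedited reporting within 24 hours "is required for reportable SAEs (including death and life-threatening events").
- Section 7.9.3: the research assistant is the sole blinded party, and "Investigators providing clinical management and decision-making are informed of each participants randomization result".

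**The concern.** Most of the named events can be dated and checked against records. A miscarriage, a pre-term birth or a child removal either happened or did not, and a significance call adds discretion without adding information. Without a criterion, two clinicians at two sites could treat the same event differently. Without masking, the same clinician could treat it differently by arm, even with no intention to do so.

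The process also looks circular. An event on the list becomes an AE once the clinician judges it significant, yet the clinician is described as seeing events that staff have already reported as AEs.

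At stake are the listings from which the study team judges whether benefit-to-risk has shifted and whether the trial should continue (section 12.0, part C), and which the DSMB receives (section 12.0, part C, and Appendix A). In a pilot of 122 women, a few events left out could change how those listings read.

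**Working it through.** The plan states no figure to reproduce here, and the point does not depend on sample size or power. The check sets the statements side by side.

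**1. Does the general definition capture the named events anyway?** It has no clinician test, but it requires the occurrence to be unexpected and medical. The Definition of Expectedness ties unexpectedness to not being listed in the protocol, or not at the observed specificity or severity. The named events are listed, and child removal is not plainly medical. On that reading, the sentence with the significance test is their main way in. The text is not conclusive: the Definition of Expectedness sorts any adverse event into expected or unexpected, which would be idle if every AE had to be unexpected already.

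**2. Is clinical significance defined?** No. Appendix A grades severity and gives a causality question, but neither says what makes a named event significant.

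**3. How does an event reach the clinician?**

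- Section 8.2.1: AEs and SAEs that suggest deterioration are escalated.
- Section 12.0, part B: AEs and SAEs that have been reported.
- Appendix A, severity and causality: reportable AEs, at least weekly.

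All three start from something already called an AE or SAE. None says how, or by when, an unclassified event is put to the clinician. The last two also differ in scope, one covering all reported AEs and the other reportable AEs only.

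**4. Is the judgement masked?** Sections 7.9.2 and 7.9.3 blind only the research assistant who does the assessments. Nothing masks the study medical clinician. Under section 8.2.1 the navigator, who delivers the intervention (section 7.5), asks about AEs.

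**5. What happens to the 24-hour clock?** Section 12.0, part A, starts it at site knowledge; Appendix A starts it at occurrence and/or site knowledge. Trained staff make the first assessment of seriousness. The clock therefore does not formally wait for the clinician. However, it applies to reportable SAEs, seriousness is defined as a property of an AE or adverse reaction, and it rests on the view of the clinician or the sponsor. If staff held an event as not yet an AE until a weekly review, the wait could reach 7 × 24 = 168 hours, against 24. That is an upper limit under a practice that the plan does not prescribe.

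**6. Do the special rules agree?** Section 8.2.1 records every reported overdose with no significance test, but allows a separate form, so an overdose can be recorded and still be missing from the AE listings. Appendix A says that a death must be reported, yet puts death in the list subject to the test.

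**7. Size.** Let r1 and r0 be the true event risks in the two arms, and a1 and a0 the shares accepted as significant. The apparent risk ratio is (r1/r0) × (a1/a0). If a1 = a0, the ratio is undistorted, although both counts are too low whenever the share is below 1. If they differ, the ratio is off by the factor a1/a0. The documents give none of these four quantities.

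**The case against.** The strongest reply is that the significance clause does less than it seems to.

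- **The test may not be exclusive.** The general definition can be read as covering medical events unaided, with the second sentence only adding changes in status such as child removal. This stands as an ambiguity, which is itself a reason to reword.
- **Overdose and death have their own rules.** A reader might infer that an overdose counts only if the clinician finds it significant. Section 8.2.1 does not support that. What remains is the separate form. A death must be reported in any case.
- **Pregnancy loss in general is not on the list.** Only miscarriage is named; other losses would fall to the general definition.
- **The 24-hour duty does not depend on the weekly review.** A reader might add the 7-day AE entry limit to the weekly review and set 14 days against 24 hours. That mixes the ordinary AE track with the SAE track. Staff rate seriousness first, and SAEs are reviewed when reported.
- **No by-arm AE comparison is planned.** Section 10.3 specifies none, and the DSMB receives listings of AEs and summaries of SAEs. Arm-dependent distortion therefore matters only when someone reads those listings by arm. Incompleteness matters either way.
- **Some events show up elsewhere.** Miscarriage ends follow-up (section 7.6), the Study Completion Form tracks status, and drug use is measured by urine toxicology and Timeline Follow Back. The plan does not say that any of these feeds the AE listings.

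The reply narrows the point. It does not supply a criterion, masking, or a route to the clinician.

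**Conclusion.** The point holds in a limited form. The significance test is undefined, the person applying it is not masked, and no route or deadline takes an unclassified event to that person. Entry into the AE listings is therefore discretionary, most clearly for miscarriage, pre-term birth and child protective services involvement. Two conflicts also need reconciling: the significance clause against the overdose and death rules, and the two descriptions of what the clinician reviews.

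A missed 24-hour report is a plausible consequence if staff wait for classification, but it is an inference; the plan does not tell them to wait. A reader might also infer that the harm counts will be biased in a particular direction. Nothing in the documents shows that acceptance would differ by arm, so neither direction nor size can be stated.

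The conclusion assumes that the significance sentence is the working route for the named events and that no operating procedure outside these documents supplies the missing criterion. It should be corrected because AE data inform decisions about continuing the trial. It does not undermine the design.

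**What to change.** Replace the significance sentence in Appendix A with wording such as:

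> *Death, miscarriage, pre-term birth, overdose, and involvement of child protective services (child removal included), if new or worsened since baseline, are AEs whenever they occur. Site staff enter each on awareness under the timelines in this appendix. The study clinician then rates seriousness, severity and causality.*

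The new-or-worsened limit keeps conditions already present at entry from being counted, which is the purpose of Appendix A's Medical and Psychiatric History section.

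In addition:

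- Amend section 8.2.1 so that an overdose recorded on a separate form is also entered as an AE or SAE.
- Keep the significance test only for other changes from baseline. State explicitly that relapse stays under it, write the criterion down, and say how and by when staff pass such changes to the clinician.
- Give one scope for clinician review in section 12.0, part B, and in Appendix A.

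The cost is a few sentences, a checklist on the AE form, and some additional AE entries, whose number cannot be estimated from the documents. Ratings of severity and causality would still be made unmasked, but whether a named event is counted would no longer depend on them.

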### Definition of Expectedness

Any adverse event is considered "unexpected" if it is not listed in the protocol, consent, or is not listed at the specificity or severity that has been observed.

## **Medical and Psychiatric History**

A thorough medical and psychiatric history during the baseline phase should record any chronic, acute, or intermittent preexisting or current illnesses, diseases, symptoms, or concerning signs of the participant, to avoid reporting pre-existing conditions as new AEs and to assist in the assessment of worsening in intensity or severity of these conditions that would indicate an AE. Stable chronic conditions, such as arthritis, which are present prior to clinical trial entry and do not worsen are not considered AEs.

## **Site's Role in Eliciting and Reporting Adverse Events**

Appropriately qualified and trained personnel will elicit participant reporting of AEs and SAEs at each study visit designated to collect AEs. Adverse events (medical and/or psychiatric) assessment will initiate with participant consent and follow-up will continue through the final assessment. Study personnel will obtain as much information as possible about the reported AE/SAE to complete the AE/SAE forms and will consult as warranted.

Standard reporting, within 7 days of the site becoming aware of the event, is required for reportable AEs. Expedited reporting (within 24 hours of their occurrence and/or site's knowledge of the event) is required for reportable SAEs (including death and life-threatening events). Local sites are responsible for reporting SAEs to the IRB of record, per the IRB or record's guidelines.

Sites are required to enter reportable AEs and SAEs in data capture program. The AE form is used to capture reportable AEs and SAEs (as defined in the protocol) and will be reviewed by the study PI upon submission. Additional information may need to be gathered to evaluate SAEs and to complete the appropriate CRFs and the summary. This process may include obtaining hospital discharge reports, medical records, autopsy records or any other type records or information necessary to provide a complete and clear picture of the serious event and events preceding and following the event. If the SAE is not resolved or stable at the time of the initial report or if new information becomes available after the initial report, follow-up information must be submitted as soon as possible.

Reportable adverse events will be followed until resolution, stabilization or study end. Any serious adverse reactions will be followed until resolution or stabilization even beyond the end of the study.

